7.1.4 Procedures

7.1.4.1 Metabolomics analyses

The metabolomics analyses will utilize mass spectrometry (MS) coupled with chromatographic separation, using two analytical approaches with broad analytical coverage. For the global profiling of polar metabolites, GC coupled to high resolution quadrupole-time-to-flight mass spectrometry (GC-QTOFMS) will be used. The analytical protocol is similar as previously developed for GC \times GC-TOFMS (94). For the analyses of molecular lipids, ultra-high performance liquid chromatography combined with quadrupole-time-of-flight mass spectrometry (UHPLC-QTOFMS) will be utilized (95).

[name] and [name], who worked together over the past eight years, have an extensive knowledge of these platforms for the analyses of clinical samples. Taken together, these two platforms allow detection of over 2000 metabolites, covering all main metabolic pathways such as lipid metabolism, central carbon metabolism, amino acid metabolism, urea cycle, ketogenesis as well metabolism, as detection of several metabolites related to nucleotide metabolism as well as gut microbial metabolism. The methodology combined targeted, quantitative approach with semi-quantitative profiling.

The lipidomics platform proposed for this study was recently assessed as part of the US National Institute of Standards (NIST) lipidomics ring study, which comprised 31 laboratories worldwide (96). Blinded NIST standard reference plasma sample (NIST SRM 1950) has been used in the study and we obtained excellent results (mostly within 10 % of consensus quantitative values), which highlights the accuracy and robustness of our lipidomics protocol.

The Department of Natural Science and Technology at Örebro University has a state-of-the-art facility for metabolomics, with several MS instruments (GC-HRMS, 2 x GC-MS, 2 x UHPLC-QqQMS, GC-QqQMS, GC-QTOFMS, UHPLC-QTOFMS, UPLC2-MS, ICP-MS), several other analytical instruments (CE, UHPLC) and three more instruments are being purchased in 2017 (GC-MS, UHPLC-IM-QTOFMS, Orbitrap MS). This infrastructure can be utilised for the further characterization of the unknown metabolic markers. We are also currently setting up a database management system, including both the infrastructure (database, software) and the personnel for the task.

7.1.4.2 Immune status analyses

Analysis of inflammatory markers and immune status will be performed using a number of well-established methods. Quantification of cytokines and other soluble markers of inflammation in plasma will mainly be performed using electrochemiluminescent ELISA technology, which enables sensitive detection coupled with a broad detection range. Furthermore, this technology allows multiplexing, which reduces the amount of material needed. To monitor the effect of rituximab on immune status, B-cells will be quantified and phenotyped using flow cytometry. Transitional, naïve, memory and regulatory B cells will be identified using a combination of markers (CD19, CD24, CD27, CD38, CD5). Gene expression analysis of inflammatory genes will be performed using a combination of DNA microarray technology and real-time qPCR.

These methods are available through collaboration with researchers at iRiSC. iRiSC is an interdisciplinary research environment that includes 10 professors and a number of junior scientist, all holding expertise in inflammatory regulation. The infrastructure includes data analysis, instruments and personnel.

7.1.4.3 Venipuncture blood collection

Blood samples will be obtained for screening and routine clinical testing, analysis of pro-inflammatory cytokines, genetic analyses and screening for biomarkers. A registered nurse or trained phlebotomist will utilize a sterile technique to draw blood by venipuncture. Up to 150 ml of blood may be obtained three times during pre-study screening, visit 7, 8 and 12 (weeks -4-0; 12, 20 and 40), and 5 ml of blood will be obtained at visit 4 and 5 (week 2 and 5). Maximum blood volume is 770 ml. From the blood samples we will obtain biomarkers of inflammatory signaling and permeability of the gut using ELISA and Mesoscale methods.

7.1.4.5 Lumbar puncture CSF collection

To evaluate CSF levels of inflammatory cytokines, a lumbar puncture (LP) will be performed as described. LPs will be done in the L3/L4 or L4/L5 interspace following administration of local anesthetic. A volume of up to 20 ml of CSF will be collected in silicone-coated tubes for research. Tubes will be gently mixed to avoid gradient effects. CSF samples will be centrifuged at 2000g, 8°C, for 10 minutes to remove cells (for gene expression analyses) and other insoluble material, aliquoted into 1 ml tubes to eliminate the need for repeated freezing and thawing, and stored at -80°C. From the CSF samples, we will obtain biomarkers of inflammatory signaling using ELISA and Mesoscale methods. Mesoscale allows for complex multiplexing of up to 17 analytes in one sample, and will be the method of choice. The lumbar puncture is optional.

7.1.4.6 Stool

The *ex vivo* Ussing chamber model, well-established in the ORU lab will be used for examining gut permeability (97). Colonic specimens obtained by distal colonoscopy in an unprepared bowel, will be mounted in Ussing chambers and the effect of mucosal application of intestinal metabolites on intestinal transfer and permeability will be assessed in conjunction with histochemical analyses of the human biopsies. In all patients, *in vivo* segmental whole-gut permeability will be assessed by measuring 24-hour urinary recovery of five specific sugar probes.

Gut microbiome. Altered gut microbiome in first episode psychosis patients has been reported. In a study by Schwartz (2018) (98), numbers of *Lactobacillus* group bacteria were elevated in first episode psychosis patients and significantly correlated with symptom severity along different symptom domains.

Stool samples are collected in the privacy of the patient's own home. A kit with three containers will be provided to collect faeces specimen that are kept in a special isolated bag. The patient is requested to place the bag in the freezer of her/his home. The bag shall be kept there until a transport is organized to the Örebro University hospital biobank by a research assistant. To provide a stool sample is optional.

7.1.4.7 Brain imaging

Patients will undergo an fMRI-based assessment lasting approximately 2 hours (optional). Prior to scanning patients will be asked to once again complete a MRI checklist. Patients will also be asked if they have taken benzodiazepines and/or hypnotics within 24 hours of initiating MRI; those who have will be asked to come back for a later session. During scanning, patients will undergo the following protocol:

1. Diffusion weighted imaging: 90 gradient orientations distributed in two shells of $b=1000$ and $b=2000$, plus 2 $b=0$ images; 2 mm resolution isotropic—20-minute scan time. We will estimate neural inflammation using a measure of regional extra-cellular free water derived from the diffusion weighted imaging data. We will apply to these data a free-water estimation algorithm that calculates the degree of cellularly constrained versus extra-cellular water. This method has been used reliably to determine levels of regional neuro-inflammation in psychiatric conditions.
2. Brain-blood perfusion imaging: arterial spin labeling scan, 40 labeled and 40 unlabeled scans, 30 axial 5-mm thick axial slices, 4x4 mm in-plane resolution—6-minute scan time.
3. Resting functional MRI (fMRI) scanning: blood-oxygen level dependent scan, SMS factor = 3, GRAPA = OFF, 32 4-mm thick axial slices with 3x3 mm in-plane resolution—12-minute scan time.
4. High-resolution anatomical MRI scans:
 - a. Whole-head, T1-weighted MRI scan, 1-mm isotropic voxels—6-minute scan time.
 - b. Whole-head, T2-weighted MRI scan, 1-mm isotropic voxels—6-minute scan time.

We will also use various fMRI paradigms for assessing social anhedonia, e.g. by studying diminished motivation for social affiliation and lack of reward from social incentives (99). Reward processing abnormalities have been implicated in pathophysiology of negative symptoms in schizophrenia, such as anhedonia and avolition. One method to study reward is to use monetary incentive delay task and affective incentive delay task (100). This paradigm has previously been used to investigate neural correlates of reward processing in substance abuse, pathological gambling, depression, schizophrenia, binge eating, and ADHD (101). The results in the patients will be compared to those of healthy controls.

7.1.4.8 Qualitative content analysis

The 12 participants from the study will be interviewed about their experiences about participating in the study, using a semi structured interview guide. The questions will be focusing on the participants' experiences about the treatment, the approach from the staff their feelings about their psychiatric diagnosis. Our hypothesis is that the patients may have other thought about their psychiatric condition as it now can be viewed as an inflammatory disorder instead of purely a mental condition. Also we are interested in if the participants have reflected on any change in the approach of the staff since they now are regarded as “somatically ill patients” not simply “psychiatric patients”. The interviews will be transcribed verbatim and analyzed with qualitative content analysis.

Table 1 Study plan

Week		
-4 – 0	Screening prior to treatment with rituximab Decision on inclusion / exclusion	
 • Evaluation of suitability • Vaccination check up (+varicella) • Information to not use attenuated vaccines, what risks are involved and signs of immunosuppression • Consent form • Information card about drug study participation • Demographics questionnaire including FTF-Brief • Treatment history • PNISSI and fine motor examination • Physical examination • Check anti-hypertensive medication* • Test for group A streptococcus • Blood sample • Routine safety: Test of hepatitis, HIV, TB and routine tests • Therapeutic drug monitoring • Urine: illicit drug screen and pregnancy test, inflammatory markers • Assessments (CGI-S and MINI, psychiatric rating scales, GAF, EQ-5D, Level 1 Cross-cutting symptom measure of global symptom severity) • Functioning: PSP and BBQ • Side-effects, AAR • UKU • Client satisfaction questionnaire (CSQ) • Cognitive tests Video recording I • Lumbar puncture (optional) • Faeces biopsy and sample (optional) • fMRI (optional)
0	Baseline Rituximab dose 1000 mg	
 • Assessments (PANSS, CGI-I**, PGE, CGI-S) • Blood sample (inflammatory markers)
2	Nurse check-up	
 • Side-effects, AAR
5, (+/- 1 week)		
 • Side-effects, AAR • Patient evaluated improvement (PGE) • Blood sample (B-cell population)
8	Nurse check-up	
 • Side-effects, AAR • Patient evaluated improvement (PGE)
12		
 • Assessments (PANSS, CGI-I**, PGE, CGI-S) • Side-effects, AAR • Patient evaluated improvement (PGE) • Blood sample (B-cell population) • Video recording II
16 (+/- 1 week)	Nurse check-up	
 • Side-effects, AAR • Patient evaluated improvement (PGE)
20-23	20 w	
Interview + Assessments (PANSS, CGI-I*, PGE, CGI-S, and MINI, psychiatric rating scales, GAF, EQ-5D, Level 1 Cross-cutting symptom measure of global symptom severity)
 
 • PSP • Side-effects, AAR

		
• UKU• Client satisfaction questionnaire (CSQ)• Physical examination• Cognitive and motor tests (from PNISSI and Nine-Hole Peg Test)• Video recording III• Blood sample• Lumbar puncture (optional)• Faeces sample (optional)• Urine sample• fMRI (optional)
20-24	Clinician	
• Extended interview for content analysis
24 (+/- 1 week)	Nurse check-up	
• Patient evaluated improvement (PGE)• Side-effects, AAR
32 (+/- 1 week)	Nurse check-up	
• Patient evaluated improvement (PGE)• Side-effects, AAR
40-43	40 w	
• Interview + Assessments (PANSS; CGI-I*, PGE, CGI-S, and MINI, psychiatric rating scales, GAF, EQ-5D)• PSP and BBQ• Client satisfaction questionnaire (CSQ)• Side-effects, AAR, UKU• Blood sample• Cognitive tests• Video recording IV
52 (+/- 1 week)	1 year follow-up	
• Assessments (PANSS, CGI-I, PGE, CGI-S, GAF)• Side-effects, AAR

*if the patient is treated with antihypertensive medication these should be withdrawn 12 h prior to the rituximab treatment

**evaluated by clinician and next-of-kin

Table 2

Week			-4 - 0	0	1	2	5	8	12	16	20	24	32	40	52
Visit			1	2	3	4 (nur se)	5	6 (nur se)	7	8 (nur se)	9	10 (nurse /other)	11 (nur se)	12	13
Activity/ Assessment number	CRF Y/N	Time to complete		Pre-Study Screening	Baseline 1:0						20w			40w	
ENROLMENT Eligibility screen, Consent form, Demographics questionnaire, Treatment history, PNISSI, Physical examination, FTF-Brief. Routine blood tests, hepatitis, HIV, TB. Vaccination check up (+varicella). Therapeutic drug monitoring, U-illicit drug screening,		60 min	x												
Pregnancy test (females)			x												
INTERVENTION Rituximab, Dose 1: 4.5h				x:1											
ASSESSMENTS MINI, Psychiatric rating scales		45 min	x								x		x	x	x
Level 1 Cross-cutting symptom measure of global symptom severity			x								x				
GAF, PSP		5 min	x							x		x		x	x
CSQ, BBQ, EQ-5D		10 min	x								x			x	
PANSS		20 min		x						x		x		x	x
CGI-S (clinician)		5 min	x	x						x		x		x	x

CGI-I (clinician and next of kin)		10 min		x				x		x			x	x
PGE (patient evaluated improvement)		5 min		x			x	x	x	x	x	x	x	x
UKU		10 min	x							x			x	
Side effect open check up questions and AAR		10 min	x			x	x	x	x	x	x	x	x	x
Blood sample		15 min	x	x		x		x		x			x	
Lumbar puncture		30 min	x							x				
Faeces sample		5 min	x							x				
Urine test (morning sample)		5 min	x							x				
fMRI		120 min	x							x				
Gut biopsy		30 min	x											
Cognitive and motor test		30 min	x							x				
Video recording		10 min	x					x		x			x	
Extended interview for content analysis		45 min								x				
Nurse in-between visits/ progress notes		10 min			x		x		x	x	x			

BBQ = Brunnsviken Brief Quality of Life Inventory; CGI-S = Clinical Global Impression-Severity scale; CGI-I = Clinical Global Impression-Improvement scale; CSQ = Client Satisfaction Questionnaire; GAF = Global Assessment of Function; MINI = Mini International Neuropsychiatric Interview; MRI = Magnetic Resonance Imaging; PGE = Patient's Global Evaluation of improvement; UKU = Udvælg Kliniske Undersøgelser, side effect rating scale; Personal and Social Performance (PSP) Scale; EuroQol Group EQ-5D; Any Adverse Reactions (AAR).

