6 SELECTION AND WITHDRAWAL OF VOLUNTEERS

6.1 Inclusion Criteria

To be eligible for inclusion into this study, each patient must fulfil all of the following criteria:

- 1) Age: 18 to 40 years
- 2) Duration of psychiatric illness: exceeding 2 years
- 3) Rated "Markedly ill", "Severely ill" or "Among the most extremely ill patients" on the Clinical Global Impression – Severity scale (CGI-S)
- 4) Global Assessment of Functioning below 50
- 5) Current diagnosis according to Diagnostic and Statistical Manual for Mental Disorders, 5th edition (DSM-5) of SSD (schizophrenia spectrum disorder)
- 6) Treatment resistance, i.e. failing to remit despite adequate treatments
- 7) If female and with any risk for pregnancy: willing to use contraceptives.
- 8) If antipsychotic treatment is prescribed the plasma concentrations of the drug must be tested and shown to be within the therapeutic interval.
- 9) Subjects should be judged by the investigator to be lucid and oriented to person, place, time, and situation when giving the informed consent.
- 10) Immunoglobulin levels within the normal range

Treatment resistance is defined as poor general functioning (GAF<50) and minor or no persistent improvement from previous treatment attempts, according to the following specifications: At least 2 trials with different evidence-based drug treatments for schizophrenia and at least one from the second generation of anti-psychotic drugs. Both drugs should have been tested for a minimum of 4 months with adequate dosages. Clozapine must have been tested or considered not feasible

Fertile women will only be included in the study if they are using/agree to use adequate contraception during treatment with the study drug and for the following 12 months after the last treatment. Adequate contraception is defined as at least 1 of the following: 1) abstinence, 2) oral contraceptive (combined or progesterone alone), 3) implants of levonorgestrel, 4) estrogenic vaginal ring, 5) percutaneous contraceptive patches, 6) injectable progestogen, 7) intrauterine device (IUD) or 8) male partner sterilization. Non-fertile women are defined as any female that is surgically sterile (documented hysterectomy and/or bilateral oophorectomy or tubal ligation).

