6.2 Exclusion Criteria

Patients are to be excluded from the trial if any of the following criteria is fulfilled:

- 1) on-going immunomodulatory treatment
- 2) pregnancy or breast-feeding
- 3) weight below 40 kg
- 4) clinically relevant on-going infection
- 5) chronic infections
- 6) positive screening test for hepatitis B, C HIV or tuberculosis
- 7) any change of psychotropic medication within the previous 4 weeks
- 8) “much” or “very much improved” already at baseline according to CGI-I i.e. scores of 1 or 2 by the clinician
- 9) severe heart failure (NYHA grade IV) or other severe heart disease or history of cardiac arrhythmia or myocardial infarction
- 10) unable to make an informed decision to consent to the trial
- 11) in compulsory treatment
- 12) treatment with clozapine within the last 2 months
- 13) previous treatments with immunosuppressive agents
- 14) malignancy currently or within 2 years prior to inclusion

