- T cell activation against selected, recombinantly produced, human, cerebral peptides, using the method FluoroSpot, where different cytokines will act as markers for T-cell activation (PBMC sample, stored in – 80° C) (application of novel findings from our group)
- Genetic analysis for identification of predisposing factors and possible outcome predictors (e.g. polygenic risk scores and single nucleotide polymorphisms (SNPs), related to relevant psychiatric disorders) by DNA microarray technology

Blood and CSF

At baseline, week 12 (blood only), 20 (blood and CSF) and week 40 (blood only):

- Inflammatory markers (e.g. IL-6, IL-1Ra, sTNFR1) and chemokines (e.g. CCL2, CXCL13), and other immune markers (e.g. sCD14, IL-10, complement C3 and C4), measured by means of electrochemiluminescence immunoassay (Mesoscale instrument), hsCRP, Neuronal damage assessment by measuring neuron specific enolase (NSE), S100, neurofilament light chain (NFL), and neurotrophic substances (brain-derived neurotrophic factor (BDNF) and glial cell line-derived neurotrophic factor (GDNF))
- Metabolomics, to explore molecular target mechanisms

Only at baseline:

- Titres of CNS-relevant autoantibodies (e.g. anti-NMDA receptor antibodies, voltage-gated calcium channel (VGCC) antibodies, transglutaminase antibodies, anti-nuclear antibodies (ANA))

CSF only

At baseline and at week 20:

- Routine tests for CSF (e.g. cell count, albumin and immunoglobulin quotients, oligoclonal bands)
- (If sufficient number of CSF cells are available): Expression levels of pro-inflammatory genes (e.g. IL-1 β , caspase, IL-6, IL-8), analysed using real-time PCR and DNA microarray technology

Microbiology

Only at baseline:

- Routine test for presence of group A streptococci infection

Faeces

At baseline and at week 20:

Faecal samples will be collected at baseline (before intervention), and week 20 (after intervention). Patients will collect two spot samples of faeces in plastic containers at home at each time point. Analyses will include:

- F-calprotectin
- Metabolome
- Microbiome; Faecal sample for quantitative and qualitative analyses of faecal microbial composition by 16S rRNA-based next generation sequencing (NGS).

Urine

Only at baseline and week 20:

Urine samples will be collected at baseline (before interventions), and week 20 (after intervention) in parallel with collection of blood. Urine will be used for:

- Screening for pregnancy prior to the rituximab treatment (week 0)

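### Tables 1 and 2 allow the only pregnancy test to be up to 28 days old at the single rituximab infusion; schedule a test at the week-0 visit

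*Combined protocol and SAP*

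**What the plan says.** Pregnancy is exclusion criterion 2 in section 6.2. Section 8.2 gives rituximab on one occasion, which both tables place at week 0.

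Three places deal with the timing of the pregnancy test:

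- **Table 1 (Study plan).** The test appears once, in the screening row for weeks -4 to 0: "Urine: illicit drug screen and pregnancy test, inflammatory markers". The week-0 row lists ratings, a blood sample and the infusion, with no urine sample.
- **Table 2.** The row beginning "Pregnancy test (females" has one mark, in the enrolment block, one column before the rituximab mark. The separate row beginning "Urine test (morning sample" is marked at screening and at one later visit.
- **Section 7.1.3, Urine.** The item reads "Screening for pregnancy prior to the rituximab treatment (week 0", with the bracket closing there. The lead-in to that list begins "Urine samples will be collected at baseline (before interventions".

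Section 6.1 covers contraception. Inclusion criterion 7 reads "If female and with any risk for pregnancy: willing to use contraceptives". The explanatory text admits fertile women only if "they are using/agree to use adequate contraception during treatment with the study drug and for the following 12 months after the last treatment".

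**The concern.** The infusion cannot be taken back, so the pregnancy status that matters is the status on the day it is given. Site staff usually work from the schedule tables. Followed literally, these are satisfied by a test at the start of screening with no repeat. Section 7.1.3 can be read as asking for a test at week 0, so the tables may be looser than the text intends.

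The contraception rule does not clearly cover the time between screening and infusion. A woman who agrees at screening to use contraception during treatment meets the wording even if she starts on the day of infusion. An early screening test together with a late start of contraception would leave an unprotected interval before the drug is given, with no later test to detect a pregnancy.

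**Working it through.** No sample-size or power figure is involved. The check sets the texts side by side and works out how old a result each one permits.

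**Inputs**

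- Screening window: weeks -4 to 0 (Table 1).
- Infusion: week 0, once (Tables 1 and 2; section 8.2).
- Pregnancy tests listed in the tables: one, at screening.
- Section 7.1 lets screening be split over more than one visit, so the day of the test within the window is not fixed.

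**Age of the result at infusion under the tables**

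- Oldest: 4 weeks x 7 days = 28 days.
- Youngest: 0 weeks x 7 days = 0 days.
- Range permitted: 0 to 28 days.

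**Age of the result under section 7.1.3**

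This depends on what the bracketed week 0 refers to.

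1. If it dates the test, the text asks for a test at the infusion visit, and the result is about 0 days old. The tables then omit something the text requires. The next item in the same list, the illicit drug screen, uses its bracket to date the test, which makes this the likelier reading.
2. If it dates the infusion, the text says only that the test comes before treatment. Text and tables then agree, but nothing in the protocol places a test at the infusion visit, and 28 days is permitted throughout.

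Under either reading, the tables permit a 28-day-old result and do not require a fresh one.

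**Contraception over the same interval**

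Section 6.1 names two periods: during treatment with the study drug, and the 12 months after it. The up to 28 days between screening and infusion belong to neither. Criterion 7 asks for willingness and has no date.

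**Number of women affected**

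The plan enrols 12 patients and does not say how many are women who could become pregnant. The number therefore lies between 0 and 12.

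**The case against.** The strongest reply is that this is imprecision and not a conflict. Most of that stands:

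- The window -4 to 0 includes week 0, so a test on the day of infusion meets Table 1, Table 2 and section 7.1.3 together.
- The bracket in 7.1.3 may date the infusion.
- The word baseline in 7.1.3 gives little support to a week-0 reading. That section also puts CSF, faeces, the drug screen and fMRI at baseline, and Table 1 lists all of these in the screening row.
- Table 2's columns are displaced in the text available for this review, so a missing mark in its urine row is weak evidence. Table 1 has to carry the point.
- Pregnancy is a binding exclusion whatever the schedule says, and section 6.1 makes contraception a condition of entry for fertile women.
- Section 7.1 names a separate infusion routine file, which was not available and may already require a test on the day.

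A reader might therefore infer that text and tables contradict each other, but the documents do not support that. They show that the tables permit an old result; they do not require one. None of these replies supplies a scheduled test at the infusion visit or a contraception start date before treatment.

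A reader might also infer that the baseline PANSS, or the CGI-I behind exclusion 8 (improvement "already at baseline according to CGI-I i.e. scores of 1 or 2 by the clinician"), could be affected by the betamethasone premedication. That dose is 12 x 0.5 mg = 6 mg, taken 1 to 2 hours before infusion, and no text orders the week-0 ratings against it. This is an argument from silence, and no effect is shown. Section 5.2 lists PANSS among scales covering the past 2 weeks, which tablets taken at most about two hours earlier are unlikely to move much. Exclusion 8 and the before-and-after comparison in section 10.1 both imply a rating before treatment. Patients who passed screening as at least markedly ill, with GAF below 50, would rarely meet exclusion 8. It is missing detail and no part of this point.

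**Conclusion.** The point holds as a minor schedule correction with a safety purpose. Tables 1 and 2 permit a pregnancy result 0 to 28 days old at a single irreversible infusion, against about 0 days on the likelier reading of section 7.1.3. Section 6.1 gives no contraception start date that covers the interval.

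The conclusion rests on two assumptions: that staff follow the tables, and that the infusion routine file does not already require a test on the day. If the file does require one, the correction only brings the tables into line with practice. The number of women concerned is not stated and cannot exceed 12. The documents give no basis for a probability that a pregnancy would be missed, so none is offered. Nothing here bears on the primary PANSS analysis.

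**What to change.** Make three changes:

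1. In Tables 1 and 2, add a urine pregnancy test at the week-0 visit for women of childbearing potential. Reword the item in section 7.1.3 so that week 0 clearly dates the test.
2. State that a negative result is required before premedication and infusion.
3. In section 6.1, start the contraception requirement at screening. This is needed alongside the week-0 test because a same-day test cannot show a very recent conception.

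The cost is one dipstick per woman concerned, at most 12, plus a few lines of wording. Section 7.1 allows premedication at home, so these women may have to take it at the clinic after the test. The screening test stays as it is.
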